## 6. Determination of Sample Size

This study treats up to 95 subjects worldwide who require replacement of their native mitral valve because of severe, symptomatic mitral regurgitation, but are at high risk for conventional mitral valve surgery. The enrollment is capped at 70 in the US, 30 in Australia, and 20 in each of France, Denmark, Finland, Greece, and the UK. The geography-specific and overall sample sizes are not statistically derived, as this is not a hypothesis-driven study.

## 7. Statistical Methods

### 7.1 Study Subjects

#### 7.1.1 Disposition of Subjects

Subject disposition will be summarized, including the number of subjects enrolled, implanted (if applicable), underwent attrition (died, explanted (if applicable), withdrew, lost to follow-up, exited the study due to other reasons), and completed each visit per follow-up schedule during the study.

#### 7.1.2 Clinical Investigation Plan Deviations

CIP deviations will be reported to Medtronic throughout the study by each site and may be identified through monitoring activities. CIP deviations will be provided in a listing and summarized by study interval and type of deviation using frequencies and percentages.

#### 7.1.3 Analysis Sets

Four analysis sets are defined for this study. The primary analysis will be based on the Approved Subjects analysis set. Analysis sets used for each objective are defined in the corresponding objective section. All data collected from consented and approved subjects will be utilized in the analyses as appropriate.

- **Consented Subjects:** Includes all subjects who signed a study informed consent. Time zero begins on the date of informed consent.
- **Approved Subjects:** Includes consented subjects who are reviewed and approved for implant by the PRC. Time zero begins on the date of informed consent.
- **Attempted Implant (Safety):** Includes approved subjects who were reviewed and approved by the PRC and entered the procedure room with the intent to attempt a TMVR procedure. Time zero begins on the date of procedure. This analysis set will be used for evaluating all safety data and clinical outcomes (i.e., NYHA, 6 Minute Walk Test (6MWT), Minnesota Living with Heart Failure Questionnaire (MLHFQ)).
- **Implanted Subjects (Hemodynamic Performance):** Composed of all attempted implant subjects with a functioning Intrepid device implanted at the time of exiting procedure room. Time zero begins on the date of procedure. This analysis set will be used for evaluating the valve performance (i.e., hemodynamics or imaging data). If the Intrepid valve is explanted or has a reintervention, then only data collected up to time of explant or reintervention are included in analysis regarding valve function.

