### 3.3 Study Population

This study will enroll and treat up to 70 subjects who require replacement of their native mitral valve because of severe, symptomatic mitral regurgitation, but are at high risk for conventional mitral valve surgery.

Patients will be screened prior to study entry to determine if they meet the Eligibility Criteria. Patients who have signed an Informed Consent and fulfill the inclusion criteria and none of the exclusion criteria listed below are eligible for enrollment.

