### **3.3.3 Patient Review Committee**

A Patient Review Committee (PRC) will consist of cardiac surgery, interventional cardiology, and echocardiology representatives who are not participating investigators. The PRC will serve in an advisory capacity to Medtronic and will review potential patients' clinical and imaging data to help ensure appropriate patient selection across all sites.

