### **Additional exploratory endpoints:**

- Measured by echo post-procedure through 5 years:
  - Reduction in MR Grade from baseline
  - No significant MV stenosis
  - LVOT outflow tract (LVOT) patency
  - Improvement in LVEF
  - Improvement in cardiac output/cardiac index
  - Reduction in LV end-systolic and end-diastolic dimensions
- Change in 6MWT from baseline through 5 years
- Change in QOL (MLHF) from baseline through 5 years
- Change in NYHA from baseline through 5 years
- Procedural times (e.g., deployment time, apical access duration, rapid pacing duration)
- Re-hospitalizations for heart failure through 5 years
- MVARC defined outcomes of: (see Appendix D for specific definitions)
  - Technical success
  - Device success
  - Procedural success
  - Individual subject success

Event and endpoint definitions for this study's analysis will be based on those definitions outlined in the MVARC Consensus Document. Each subject's data will be reviewed individually and case summaries for all subjects will be provided to FDA. The data analysis will include all subjects who undergo the TMVR procedure and all available follow-up data (e.g., key echocardiographic measures and subjects status) at each post-procedure interval.

Study results will be summarized using standard descriptive statistics. However pre-defined statistical "success" or "pass" criteria for the study endpoints are not applicable for this feasibility study, as it is not a powered, hypothesis driven study. Baseline demographic and clinical variables will be summarized. Continuous variables will be summarized with means, standard deviations, medians, interquartile ranges, minimums, and maximums. Categorical variables will be summarized with frequencies and percentages.

The sample size is based upon industry standards for pilot stage studies of medical devices; the sample size was not statistically derived, as this is not a hypothesis-testing study.

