## 7.9 Evaluation of Objectives

### 7.9.1 Primary Safety Endpoint

- Implant or delivery related SAEs (through 30 days post-procedure)

Hypothesis/Decision Criteria:

No specific hypotheses or pass/fail criteria have been set. The analysis will be descriptive and no statistical hypothesis tests are planned.

Endpoint Definition/Parameters to Be Estimated:

The severity and relationship of an AE to the implant and delivery are collected on the AE CRFs. AEs are coded using MedDRA coding. AE are reported by sites and may be reviewed and adjudicated by the CEC. An AE through 30 days post-procedure is one that occurs between day 0 (the date of index procedure) and the 30th day after the index procedure.

An implant or delivery related SAE is defined as follows.

If site AE CRF indicates the following:

- “Serious adverse event?” is answered “Yes”.
- “Relation to the TMVR device/procedure” is answered either “Possibly related”, “Probably related”, or “Definitely related”.

However, if the event was reviewed and adjudicated by the CEC, then the seriousness and relationship recorded by the CEC will be used instead.

Data Collection and Analysis Dataset:

Data will be collected on AE CRFs. Analysis will be performed on the Attempted Subjects analysis set.

Analysis Method:

The number of events, the number and proportion of subjects who have at least one SAE recorded as TMVR device/procedure related and its associated 95% exact confidence interval will be reported.

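### The pilot SAP makes committee approval a condition of its safety set, although CIP-1403 makes the committee advisory and promises to analyse everyone treated

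*Combined protocol and SAP*

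**What the plan says.** The point concerns the transapical pilot study: CIP-1403 and its SAP, version 4.0.

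**SAP.** Section 7.1.3 defines the Attempted Implant (Safety) set thus: "Includes approved subjects who were reviewed and approved by the PRC and entered the procedure room with the intent to attempt a TMVR procedure". On its use it says: "This analysis set will be used for evaluating all safety data and clinical outcomes". The Implanted Subjects set is drawn from it. For the primary safety endpoint, Section 7.9.1 states: "Analysis will be performed on the Attempted Subjects analysis set". I read that as the same set under a shorter name. Section 7.1.3 also says: "The primary analysis will be based on the Approved Subjects analysis set". The definition of that set is: "Includes consented subjects who are reviewed and approved for implant by the PRC".

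**CIP-1403.** Under Section 3.3, patients who have consented and "fulfill the inclusion criteria and none of the exclusion criteria listed below are eligible for enrollment". Section 3.3.3 describes the committee's role: "The PRC will serve in an advisory capacity to Medtronic". SAP Section 5.2 repeats both statements in substance. On the analysis population, CIP-1403 Section 7 says: "The data analysis will include all subjects who undergo the TMVR procedure". SAP Section 7.12 declares the SAP's analyses to be in line with CIP-1403.

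**The concern.** A safety denominator should follow from exposure. Here it also depends on an earlier opinion about the patient's suitability, given by a body whose agreement the supplied CIP does not require before treatment. A patient could meet the eligibility rules, be treated, have a device-related SAE, and still be outside the set on which the primary proportion is calculated.

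The gap would carry further than the primary endpoint. Section 7.1.3 assigns all safety data and clinical outcomes to this set, Section 7.9.3 uses it for the MVARC composites, and the echo endpoints use the Implanted set nested in it. The study is single-arm, SAP Section 5 has its results read against historical literature, and Section 7.8 plans an interim analysis for a CE submission. Who is in the denominator therefore matters even though nothing is tested.

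**Working it through.** **Step 1. Follow one treated subject without documented PRC approval.**

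| Question | Where | Answer |
|---|---|---|
| Eligible for enrollment? | CIP-1403 3.3 | Yes, on consent plus criteria; PRC approval is not listed |
| Can the PRC bar treatment? | CIP-1403 3.3.3, SAP 5.2 | No such power is stated; it advises the sponsor |
| In the CIP's analysis population? | CIP-1403 7 | Yes, by having the procedure |
| In Approved Subjects? | SAP 7.1.3 | No |
| In Attempted Implant (Safety)? | SAP 7.1.3 | No |
| In Implanted Subjects? | SAP 7.1.3 | No, since it is nested in the attempted set |
| In the primary endpoint? | SAP 7.9.1 | No |

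The outcome is the same whichever set is taken as primary, because Approved Subjects also requires PRC approval. Section 7.1.3 has a general sentence about using data from consented and approved subjects where appropriate, but it does not override the set named for a particular endpoint.

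**Step 2. Size.** The plan gives no figure to reproduce. SAP Section 6 gives up to 95 treated worldwide and says that this number is not statistically derived. Event counts and the number of unapproved subjects are not given, so those below are assumptions.

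Let n be the subjects attempted and x those with at least one related SAE. Let k be those attempted without approval, and e the number of those k with an event.

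- Proportion by exposure: x / n
- Proportion under the SAP rule: (x − e) / (n − k)
- The SAP figure is lower exactly when n(x − e) < x(n − k), that is, when e / k > x / n.

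So the direction depends only on whether the unapproved subjects had events more or less often than the whole group.

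Take n = 95 and x = 19: 19/95 = 20.0%, exact 95% CI 12.5 to 29.5 (Clopper-Pearson, since Section 7.9.1 specifies an exact interval).

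| k | All k had events (e = k) | None had events (e = 0) |
|---|---|---|
| 0 | 20.0% | 20.0% |
| 1 | 18/94 = 19.1% (11.8 to 28.6) | 19/94 = 20.2% (12.6 to 29.8) |
| 3 | 16/92 = 17.4% (10.3 to 26.7) | 19/92 = 20.7% (12.9 to 30.4) |
| 5 | 14/90 = 15.6% (8.8 to 24.7) | 19/90 = 21.1% (13.2 to 31.0) |

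With k = 5 and e = 1 the figure is 18/90 = 20.0%, unchanged.

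**Step 3. Other assumed rates, k = 5.** At 10/95 = 10.5% the range runs from 5/90 = 5.6% to 10/90 = 11.1%. At 29/95 = 30.5% it runs from 24/90 = 26.7% to 29/90 = 32.2%.

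**The case against.** The best defence is that PRC review was the planned route for every patient. CIP-1403 Section 3.3.3 has the committee look at potential patients' clinical and imaging data to support selection at all sites, the sponsor controls the devices, and the SAP treats approval as a stage between consent and procedure. If everyone treated was approved, the condition is redundant. Nothing in the documents contradicts that, but nothing guarantees it either. If it is true, removing the condition changes no result.

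Several stronger readings are tempting, and the documents do not support them.

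- **That the safety rate is biased in the device's favour.** No document shows anyone treated without approval. A favourable shift needs the unapproved subjects to have had events more often than the rest. That is plausible for a patient whose suitability was doubted, but much less so for one whose review was simply not filed.
- **That such subjects' events would disappear.** SAP Section 7.2 provides case summaries for all subjects to FDA, and Section 7.1.2 lists any CIP deviation recorded for them. These subjects would be missing from the primary proportion and its interval, but not from all reporting.
- **That the protocol-exception route is a source of unapproved subjects.** CIP-1403 Section 4.10 covers variances in treatment procedures and does not mention the PRC.
- **That no version of the CIP requires PRC approval.** The supplied text caps enrollment at 70, which matches the US cap in SAP Section 6. For the other geographies only the eligibility comparison in SAP Appendix 10.1 is available, so their wording on the PRC cannot be checked.
- **That the transseptal early feasibility study has the same problem.** Its plan uses a Screening Committee with the final decision on eligibility.

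It is also fair to say that the shift is modest against the imprecision. The largest fall in the 19/95 illustration is 20.0 − 15.6 = 4.4 points, against an interval 29.5 − 12.5 = 17.0 points wide, and there is no pass/fail criterion. That limits the consequence. It does not justify a rule that can drop exposed subjects from the primary safety endpoint.

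**Conclusion.** The inconsistency stands on the text. The SAP's safety set and the Implanted set within it require PRC approval, while the supplied CIP-1403 treats the committee as advisory and commits to analysing all who undergo the procedure. On this point the alignment claimed in SAP Section 7.12 does not hold.

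The consequence is conditional. It is zero if every treated subject had documented approval. Otherwise, under the assumed 95 treated, 19 events and one to five unapproved subjects, the reported proportion could lie anywhere from 15.6% to 21.1% instead of 20.0%. The shift would be favourable only if the unapproved subjects had events at a higher rate than the whole group. The set should be redefined because the change is nearly free and makes the denominator depend on exposure, not because bias has been shown.

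**What to change.** In SAP Section 7.1.3:

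1. Define Attempted Implant (Safety) as every consented subject taken into the procedure room for a planned TMVR attempt, regardless of whether the PRC reviewed the case or what it concluded.
2. Derive Implanted Subjects from that set.
3. Keep PRC approval only in the definition of Approved Subjects.
4. Reconcile the sentence that bases the primary analysis on Approved Subjects with Section 7.9.1, which uses the attempted set for the primary endpoint.

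In the disposition summary (Section 7.1.1), add a count of subjects attempted without documented PRC approval. That line tells the reader whether the point has any numerical effect. An analysis restricted to PRC-approved subjects can be kept as a sensitivity analysis if wanted.

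The cost is one reworded definition, the reconciling edit and one table line, documented as Section 7.12 requires. The reported rate may change slightly in either direction, and will not change if no treated subject lacked approval.

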## 7.2 General Methodology

A comprehensive analysis of the pilot study results, as a whole, will be assessed to evaluate the overall risk/benefit balance for the patient population being treated. Pre-defined statistical “success” or “pass” criteria for the study endpoints are not applicable for this pilot study, as it is not a powered, hypothesis-driven study.

Each subject’s data will be reviewed individually and case summaries for all subjects will be provided to the FDA. In addition, descriptive statistics will be used to summarize the preoperative, operative, discharge, and follow-up clinical data. No statistical hypothesis tests are planned. The endpoint measures will be summarized by time point. Additionally, change from baseline will be presented for each outcome, as applicable.

To report the distributions of continuous variables, mean, standard deviation, minimum, median, first and third quartiles, and maximum will be presented. To report the distributions of categorical variables, counts and proportions will be provided. Proportions and associated 95% confidence intervals will be reported for endpoints, as applicable. For time to event data, Kaplan-Meier event rates will be presented at clinically meaningful post-operative time intervals, for instance, 30 days, 183 days, and annually thereafter (e.g., 365, 365×2, 365×3 days, etc.). At each time point with data, the product-limit estimate of the event rate, the number of subjects at risk, the number of subjects with events, the Greenwood standard error of the estimate, and the loglog transformed 95% confidence interval using the Greenwood standard error will be presented.

For subjects without an event, the date of censoring will be the latest date of all follow-up visits (including video contact, phone and/or mail correspondence), assessments, events (including death in those endpoints where death is not the endpoint) and study exits. For subjects whose exit reason is lost to follow-up, the last follow-up date will be the latest date of the follow-up visits (including video contact, phone and/or mail correspondence), assessments and events.

For analyses reporting the function of the study valve using echocardiographic or MDCT data, only data corresponding to the implanted study valve will be used; data post-explant or after reintervention in which the index study valve is no longer functioning will be excluded from the analysis.

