## Data Collection and Analysis Dataset:

Data for this endpoint are collected on the procedure CRF. Data will be summarized on the Attempted Subjects analysis set.

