#### Data Collection and Analysis Dataset:

Data will be collected on the core lab echo CRF (either TTE or TTE data, whichever demonstrates a higher MR grade, will be used). Analysis dataset is the Implanted Subjects analysis set.

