#### Data Collection and Analysis Dataset:

Data will be collected on the screening and follow-up CRFs. Data will be summarized on the Implanted Subjects analysis set.

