## 7.12 Changes to Planned Analysis

The planned analyses in this SAP are aligned with the planned analyses noted in CIP-1403. Any change to the planned analyses made prior to performing the analyses will be documented in a protocol revision prior to performing the analyses. Any change to the planned analyses made after performing the analyses will be documented in the clinical study report along with a reason for the change.

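### Pilot Study SAP: the echo performance rates (MR, stenosis, LVOT patency) are conditional on an undefined 'functioning' valve at room exit, and no secondary performance endpoint counts a later explant or reintervention as a failure

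*Combined protocol and SAP*

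**What the plan says.** This point concerns the transapical Pilot Study (CIP-1403) and its SAP, not the transseptal early feasibility protocol in the same file.

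- **Set definition.** SAP 7.1.3 defines Implanted Subjects as "Composed of all attempted implant subjects with a functioning Intrepid device implanted at the time of exiting procedure room". If the valve is explanted or has a reintervention, "then only data collected up to time of explant or reintervention are included in analysis regarding valve function".
- **A second cut rule.** SAP 7.2 is narrower: "data post-explant or after reintervention in which the index study valve is no longer functioning will be excluded from the analysis".
- **Where the set is used.** In SAP 7.9.2, for each of MR grade, mitral stenosis and LVOT patency: "Analysis dataset is the Implanted Subjects analysis set". In SAP 7.9.3, for the echo endpoints through 5 years: "Data will be summarized on the Implanted Subjects analysis set".
- **Where it is not used.** For access, delivery and retrieval (SAP 7.9.2, secondary) and for MVARC device success (SAP 7.9.3, exploratory): "Data will be summarized on the Attempted Subjects analysis set".
- **The protocol.** CIP-1403 section 7 states: "The data analysis will include all subjects who undergo the TMVR procedure and all available follow-up data", with key echo measures as an example. SAP 7.12 states: "The planned analyses in this SAP are aligned with the planned analyses noted in CIP-1403".
- **Missing data.** Under SAP 7.4 a subject without data is left out of that analysis, and nothing is imputed.

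**The concern.** Entry to the Implanted set depends on something close to the outcome being measured. If *functioning* means performing acceptably, a valve left in place that leaks or narrows the outflow tract never enters the leak and outflow tables. After exit, a valve that fails and is explanted leaves the denominator at that point. The denominator therefore shrinks as valves fail, although durability of valve function is part of the secondary objective (SAP section 4).

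The absence of hypothesis tests does not make this harmless. SAP section 5 says results will be read against historical literature on surgical and transcatheter mitral treatment, and SAP 7.8 plans interim analyses for a publication and a CE submission. In such comparisons, the denominator decides what the percentage means.

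**Working it through.** The SAP gives no figure to reproduce: the sample size is not statistically derived (SAP section 6) and no test is planned (SAP 7.2). The check is to trace how each kind of failure is handled, and then to show what the denominator does to a rate.

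**Step 1. Tracing the failures.**

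| Subject | MR, stenosis, LVOT (secondary and 5-year) | Delivery of implant (secondary) | MVARC device success (exploratory) |
|---|---|---|---|
| No implant, or conversion to open valve replacement | Not in the set | Failure | Failure |
| Valve in place but poor at exit | Depends on the meaning of *functioning* | Success | Failure if the leak, MR/stenosis or complication component is met |
| Later explant | Counted up to explant, then absent | Success | Failure, kept in the denominator |
| Valve reintervention, index valve still working | Absent under 7.1.3, retained under 7.2 | Success | Failure, kept in the denominator |

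The last two rows show that no secondary performance endpoint registers a later explant or valve reintervention as a failure. The last row also shows that SAP 7.1.3 and 7.2 give different data for the same subject.

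**Step 2. Size.** Inputs:
- N = 95, the maximum treated (SAP section 6), taken here as the number attempted.
- e = subjects with no functioning valve at exit plus those explanted or reintervened before the visit. The documents do not give e, so the values below are assumptions.
- p = proportion meeting the criterion among evaluable valves, also assumed.
- No deaths from other causes and no missing echo, for simplicity.

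SAP rate = p. Rate with the excluded subjects counted as not met = p(N − e)/N. Difference = p·e/N. Intervals are exact (Clopper-Pearson) 95%.

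| N | e | SAP rate | All attempted | Difference (points) |
|---|---|---|---|---|
| 95 | 0 | 95/95 = 100% | 95/95 = 100% | 0 |
| 95 | 2 | 93/93 = 100% (96.1–100) | 93/95 = 97.9% (92.6–99.7) | 2.1 |
| 95 | 4 | 91/91 = 100% (96.0–100) | 91/95 = 95.8% (89.6–98.8) | 4.2 |
| 95 | 10 | 85/85 = 100% (95.8–100) | 85/95 = 89.5% (81.5–94.8) | 10.5 |
| 95 | 10 | 81/85 = 95.3% (88.4–98.7) | 81/95 = 85.3% (76.5–91.7) | 10.0 |
| 50 (first interim, SAP 7.8) | 4 | 46/46 = 100% (92.3–100) | 46/50 = 92.0% (80.8–97.8) | 8.0 |

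**The case against.** A reader might infer that the worst failures vanish from device performance altogether, or that no MR, stenosis or LVOT result includes them. The documents do not support either reading. Delivery of the implant is itself a secondary performance endpoint on the Attempted set, and it counts non-implant and open conversion as failures. Device success counts explant and valve reintervention as failures and keeps them in its denominator. SAP 7.9.3 also reports each of its components on the Attempted set at discharge, 30 days and later visits. Those components include MR reduction without significant stenosis, paravalvular leak, malposition and interaction with other intracardiac structures. That part of the objection stands, with three limits:

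- The MVARC endpoints are exploratory and listed only in the US and French CIPs (SAP 7.9.3).
- Component denominators use non-missing data, so a subject never implanted, or explanted with no valid later echo, can still drop out of the MR/stenosis component.
- The outflow-tract component is an event coded by the events committee, not the core-lab patency rate.

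Nor do the documents prove that leaking valves are excluded. *Functioning* may mean only that the study valve is the working valve, and the MR scale in SAP 7.9.2 allows for worsening by up to four grades inside this set. The wording is ambiguous, which is why it needs changing.

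Dropping echo data after explant is sound, because those images no longer show the study valve. Data before explant are kept, so poor function seen earlier still counts. The gap is only that the event itself is not carried.

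The CIP sentence on the analysis population is general and does not prescribe a denominator for every endpoint. It sits badly with the Implanted set but does not prove a breach of SAP 7.12.

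Finally, calling a subject with no study valve an LVOT failure would mislabel the event. This is right, and it governs how the added row must be worded.

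**Conclusion.** The point holds for the echo endpoints and no further. The MR, stenosis and LVOT rates describe valve function among subjects who left the room with a valve judged to be working and who still have it. They are legitimate as conditional haemodynamics but optimistic if read as the device's performance in everyone treated. The contrary evidence sits in the delivery endpoint and in exploratory composites, not beside the rate.

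The size rests on the unknown number excluded. At N = 95 with every evaluable valve successful, it is 2.1 points for 2 exclusions and 10.5 points for 10, and nothing if nobody is excluded. The same number of exclusions weighs more at the 50-subject interim. The conflict between SAP 7.1.3 and 7.2 and the missing definition of *functioning* need correcting whatever the counts turn out to be.

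**What to change.** 1. In SAP 7.1.3, delete *functioning*, so that every subject leaving the procedure room with an Intrepid valve in place belongs to the Implanted set.
2. Reconcile 7.1.3, which cuts valve data at any reintervention, with 7.2, which cuts only when the index valve no longer functions.
3. Keep the Implanted-set tables and label them as conditional haemodynamics. For each of MR below 2+, no significant stenosis and LVOT patency, add one supplementary row per visit on the Attempted set, labelled 'study valve in place and criterion met'. Count no implant, procedural death, explant, or loss of index-valve function at reintervention as not met. State which window procedural death uses, since SAP 7.9.3 takes day 0 for technical success and 30 days for device success. The label must make clear that the row is not an MR or LVOT measurement in subjects with no study valve.
4. Beside the row, show later deaths and other exclusions by reason at each visit. The SAP already shows deaths before the visit for NYHA class.

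This is a cheap improvement. Implant status and conversion are on the procedure CRF, and explant and reintervention on the AE CRF, so no new data collection appears to be needed. The cost is a few table rows and somewhat less favourable rates.
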